Ironically, the leading causes of MSKIs are same activities that leaders deliberately conduct to develop physical resilience: running, foot marching, other physical fitness training activities (besides running) and work-related tasks (Roy et al., 2021). Although physical training results in the highest number of total injuries, obstacle courses and ruck marching have greater injuries per exposure (Lovalekar et al., 2021). Other common causes of MSKIs include overexertion, falls/slips, and accidental injury (Army Public Health Center, 2021).

Lower back injuries are a common occurrence in athletes and sports programs. They are especially common in sports in which athletes train strength and power movements, such as powerlifting and weight lifting (Bengtsson, 2018; Reichel, 2019; Stromback, 2018). Tactical athletes-referring to firefighters, police officers, and military servicemembers- report similar prevalence of low back pain (LBP), often due to heavy equipment worn or carried for their jobs (Roy, 2021). In the US military, musculoskeletal (MSK) injuries are highly prevalent and costly in lost duty days, depleted readiness to deploy, and medical expenses(Grimm, 2019; Teyhen, 2018).

Researchers have identified multiple physical and behavioral MSKI risk factors including prior injury, female gender (Hearn et al., 2021; Kucera et al., 2016), high or low BMI (Lovalekar et al., 2021; Rappole et al., 2017), history of smoking, low aerobic endurance (Molloy, 2016; Rappole et al., 2017),

and (to a lesser extent) muscular strength and endurance (Jones et al., 2017). Unit leaders and military trainers have used these study outcomes to develop injury prevention and training program including physical fitness programs, MSKI risk screening and leader education with mixed results (Canham-Chervak et al., 2015; Lovalekar et al., 2021; Molloy, Pendergrass, Lee, Hauret, et al., 2020; Terry et al., 2018).

These epidemiological and correlational studies summarize the dilemma: Soldiers with prior injury and lower fitness levels tend to get injured (again) while training to improve their physical fitness. It is possible that other modifiable risk factors exist that, if trained, do not carry such high injury risk.

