Performance effects resulting from the messages provided to athletes shouldn't be ignored, and this is referred to as placebo (has a perceived positive effect) or nocebo (has a perceived negative effect (Horvath, 2021). The concept of performance decline after negatively-perceived stimulus has a less robust presence in the literature than placebo effects, though this is evolving. Numerous recent studies have now documented the significant detriments to physical performance when subjects are exposed to negative or potentially threatening information (Cook, 2012; Corsi, 2019; Emadi Andani, 2015; Horcajo, 2019; Jackson, 2005; Pollo, 2012; Zech, 2019).

To our knowledge, there are no longitudinal studies evaluating the risk of injury from deadlifting with a flexed lumbar spine resulting in no clear evidence that a flexed spine is a risk factor for injury. However, it is well documented that information related to potential threat (nocebo) can adversely affect physical performance. Our research aim is to determine if cautionary information about the risk of spine injury harms performance on a maximum strength test compared to a message of spine resiliency. The cautionary education is similar to standard information provided to many servicemembers before the start of an ACFT or a maximum deadlift.

9.3

Objectives/Specific Aims/Research Questions:

Describe the purpose and objective(s) of the study, specific aims, and/or research questions /hypotheses

1. Determine if general self-efficacy is a predictor of injury during Cadet Basic Training(CBT) by performing a Kaplan-Meier Survival Curve of a single self-efficacy assessment (Cadet General Self-Efficacy Assessment) and injury occurrence using the Defense Medical Surveillance System (DMSS), Cadet Illness and Injury Tracking System (CIITS), Armed Forces Health Longitudinal Technology Application (AHLTA) and a follow-up self-reported injury assessment.

1. Independent Variable: Cadet General Self-Efficacy score

2. Dependent Variables: Injury report according to CIITS, AHLTA, DMSS, sick call report or self-reported

2. Determine if task-specific self-efficacy is a predictor of injury during specific CBT events by performing a Kaplan-Meier Survival Curve, a single assessment of cadet task-specific self-efficacy and injury occurrence using DMSS, CIITS, AHLTA and a follow-up self-reported injury assessment.

1. Independent Variable: Cadet Task-Specific Self-Efficacy score

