Researchers inside and outside of the military have also found that self-efficacy predicts both performance and is negatively correlated with MSKI (Gruber et al., 2009; Samuels et al., 2010). In a study on Navy SEAL training resilience, researchers found that successful graduation was related to physiological markers of resilience (Ledford et al., 2020). However, few studies have investigated the combined effects of physical, behavioral and psychological factors on predicting MSKIs.

Cadet basic training (CBT) at the United States Military Academy (USMA) is a 7-week initial-entry training event that physically and psychologically prepares cadets to become officers. It includes similar training events and physical demands as other initial-entry military courses such as a 12-mile foot march with 35 lbs., physical training including running multiple days per week, weapons familiarization, and basic tactical training. The injury risk factors for cadets attending CBT are similar to trainees attending U.S. Army Basic Combat Training and regular military training even though injury incidence is lower (Hearn et al., 2021). Identifying self-efficacy as an injury risk factor is the first step to designing and implementing injury prevention measures. The purpose of this study is to investigate relationships between performance, MSKI and self-efficacy alone and in combination with other MSKI risk factors in USMA cadets participating in CBT.

There is currently an emphasis in Army Doctrine (FM 7-22) on form/technique for events on the ACFT, especially the maximum deadlift (MDL) and the prevention of lower back injuries. The rationale behind this is due to the perception that breakdowns in form during the deadlift lead to injuries, however, the research does not support this. Specifically, the research is unclear regarding the position of the spine while deadlifting- neutral vs flexed. Our results could impact future DoD publications regarding technique on the MDL and de-emphasize the role of a rounded spine as a safety concern.

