The researchers hypothesize that self-efficacy (general and task-specific) will be positively correlated with successful completion and performance and negatively correlated with MSKI risk during CBT. The researchers will also explore the relationship between self-efficacy and other known injury risk factors. Furthermore, we hypothesize that such beliefs about the vulnerability of the spine to injury might contribute to future disabling beliefs about back pain. This research marks an important step in investigating the role of beliefs about the back and readiness.

10.0

Study Procedures, Data Management, and Privacy

10.1 Study Procedures:

Describe step-by-step how the study will be conducted from beginning to end

Phase I: Consent and Self-Efficacy Assessment

All new cadets are eligible to participate in this study and will receive verbal and written study description during the first or second week of cadet basic training. Immediately after consenting to participate, they will complete the study demographic data information and the Cadet Basic Training Projective Performance

Invent01y, which assesses self-efficacy measured prospectively via questionnaire on a 10-point Likert scale from 1 (no confidence) to 10 (fully confident) for overall performance during cadet basic training, marksmanship/live fire training, mock marching 12 miles, land navigation, swimming, and the Army Combat Fitness Test. It will also assess for any recent injuries and whether the injury is currently hindering them.

Phase 2: Injury Surveillance During Cadet Basic Training

These researchers will monitor the Cadet Injury and Illness Tracking System (CIITS), Armed Forces Health Longitudinal Technology Application (AHLTA) and the Defense Medical Surveillance System (DMSS) up to weekly to track injuries for the duration and for up to 9 weeks afterwards. They will classify injuries as by diagnosis, region, and impact on training ("not injured" (1), "injured-not limited" (2), "injured-modified training" (3) and "injured-limited" (4)). Cadets will initially be defaulted as "not injured" (1). They will also complete the Single Assessment Numeric Evaluation (SANE), rating their current ability level on a scale of 0-100% with regards to their injury.

Phase 3: Maximum Deadlift and Low Back Pain Education

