11.0 Statistical/Data Analysis Plan

11.1 Statistical Considerations:

List the statistical methods to be used to address the primary and secondary objectives, specific aims, and/or research hypotheses. Explain how missing data and outliers will be handled in the analysis. The analysis plan should be consistent with the study objectives. Include any sub-group analyses (e.g., gender or age group). Specify statistical methods and variables for each analysis. Describe how confounding variables will be controlled in the data analysis

To determine the effect of low back pain education (cautionary vs resiliency) on deadlift performance (weight lifted), we will use ANOVA and planned comparison analysis if between-group differences are found between groups.

To determine the effect of low back pain education on deadlift self-efficacy, we will analyze change scores with a one-way ANOVA and planned comparisons if significant.

To determine the effect of low back pain education on perceived spine vulnerability, we will analyze change scores with a one-way ANOVA and planned comparisons if significant.

Our study design accounts for some confounding factors by utilizing randomization. Potentially confounding variables should be balanced between groups. We will test groups at baseline to ensure they are similar among important characteristics. Furthermore, characteristics that are different among groups at baseline or that appear to be influential on load lifted will be included in the ANOVA model as a covariate to control for and test for potential confounding.

11.2 Sample Size:

1200 participants

11.3 Total number of subjects requested (including records and specimens):

1200

11.4 If you are recruiting by study arm, please identify the arms of the study and how many subjects will be enrolled in each arm

N/A

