11.5 Please provide a justification for your sample size

We have powered this study to determine a between-group difference of 5kg. This is equivalent to an effect size of $d=.10$ given a standard deviation of 23kg (available from previously collected data in this lab). We used G*Power 3.0 with power at .80 to calculate a total sample size of 969 subjects (323 per group). We will therefore attempt to recruit 1200 participants, allowing for 20% injury or attrition which might prevent subjects from completing the MDL event during CBT ACFT.

11.6 Data Analysis Plan: Complete description: Background, Objectives, Design, Step by Step how the project is going to be done, Data analysis plan:

1. Determine if general self-efficacy is a predictor of injury during CBT by performing a Kaplan-Meier Survival Curve, a single assessment (Cadet General Self-Efficacy Assessment), analysis of the Defense Medical Surveillance System (DMSS) and a follow-up self-reported injury assessment.
 1. Independent Variable: Cadet General Self-Efficacy score
 2. Dependent Variables: Injury report according to DMSS or self-reported
2. Determine if task-specific self-efficacy is a predictor of injury during specific CBT events by performing a Kaplan-Meier Survival Curve, a single (or multiple) assessments of cadet task-specific self-efficacy, analysis of the Defense Medical Surveillance System (DMSS) and a follow-up self-reported injury assessment.
 1. Independent Variable: Cadet Task-Specific Self-Efficacy score
 2. Dependent Variables: Injury report according to DMSS or self-reported
3. Determine if general self-efficacy is a predictor of performance during CBT by performing a multivariate regression between a single assessment (Cadet General Self-Efficacy Assessment) and multiple measures of performance during CBT including 1) successful completion (pass/fail), 2) Army Combat Fitness Test (ACFT) raw or calculated score, 3) Warrior Competition performance, 4) marksmanship score, 5) written exams, 6) swimming assessment and 7) any other individually graded events.
 1. Independent Variable: Cadet General Self-Efficacy score
 2. Dependent Variables: performance outcome by event- 1) successful completion (pass/fail), 2) Army Combat Fitness Test (ACFT) score, 3) Warrior Competition performance, 4) marksmanship score, 5) written exams, 6) swimming assessment and 7) any other individually graded events.

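### For injury (Objectives 1 and 2) the plan names only a Kaplan-Meier curve on the self-efficacy score, which forces the score into groups and leaves the aim of studying it together with other risk factors without an analysis

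*Combined protocol and SAP*

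**What the plan says.** Section 11.6, item 1, sets out to "Determine if general self-efficacy is a predictor of injury during CBT by performing a Kaplan-Meier Survival Curve". Section 9.3, item 1, has nearly the same text: "Determine if general self-efficacy is a predictor of injury during Cadet Basic Training(CBT) by performing a Kaplan-Meier Survival Curve". Item 2 in both sections names the same method for task-specific scores. The score is the only independent variable in each.

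Section 9.6 (Benefit to the DoD) gives a wider purpose: to "investigate relationships between performance, MSKI and self-efficacy alone and in combination with other MSKI risk factors". It adds "Identifying self-efficacy as an injury risk factor is the first step to designing and implementing injury prevention measures", and the hypotheses at its end say "The researchers will also explore the relationship between self-efficacy and other known injury risk factors". No method is attached to either statement of the wider aim.

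On risk factors, section 9.2 says "Researchers have identified multiple physical and behavioral MSKI risk factors including prior injury, female gender" and continues with "high or low BMI", smoking history and low aerobic endurance. Section 10.2 collects gender, height, weight and injury within the last year.

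The only covariate rule is in section 11.1: "characteristics that are different among groups at baseline or that appear to be influential on load lifted will be included in the ANOVA model". It concerns the deadlift.

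**The concern.** A Kaplan-Meier curve describes time to injury in groups. Three things follow.

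- The 1-10 score (section 10.1, Phase 1) has to be cut into groups, and no cut is given. Grouping discards information, and the curve yields no effect per point.
- A curve by score group can address self-efficacy on its own. It cannot show what the score adds to prior injury, gender or BMI, which is part of the stated purpose.
- Randomization, which section 11.1 relies on against confounding, does not help here. The education message is allocated; self-efficacy is only observed.

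At stake is how the result will be used. Section 9.6 treats a finding on self-efficacy as the start of prevention work, and section 14.4 foresees training that develops self-efficacy. If the score mainly reflects injury history, the unadjusted curve would still separate the groups, and a reader could not tell the difference.

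**Working it through.** **1. Is there an injury model elsewhere?** Going through every stated analysis:

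| Objective | Outcome | Method |
|---|---|---|
| 1, 2 | injury | Kaplan-Meier curve, score only |
| 3, 4 | performance in CBT | multivariate regression |
| 5 | sources of self-efficacy | chi-square |
| 6, 8, 9 | weight lifted, change scores | one-way ANOVA |
| 7 | deadlift confidence and weight lifted | paired t-test, multiple regression |

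No analysis of injury has a second predictor. The plan gives no event count, hazard ratio (HR) or power for injury, so there is no figure to reproduce. Its one computed sample size (969) belongs to the deadlift comparison.

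**2. Loss from grouping.** Assume a normal score and a median split. The share of information kept is the squared correlation between score and split: (0.3989 / 0.5)² = 2/π = 0.64. About 36% is lost.

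With 1200 cadets (section 11.2) and an assumed 20% injured there are 240 events. For 80% power at two-sided 5%:
- continuous score: ln HR per SD = 2.80 / √240 = 0.181, so HR 0.83
- median split: 2.80 / √(240 × 0.64) = 0.227, so HR 0.80

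At an assumed true HR of 0.85 per SD without confounding, simulated power was 67-70% for the continuous score and 47-53% for the split. With 10% injured it was 43% against 28%; with 30% injured, 86% against 64%. The loss depends on the cut: a trend over tertiles gave 57% at 20% injured, against 50% for the split and 70% for the continuous score in the same runs.

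**3. Confounding, worked by hand.** All inputs are assumed. Let 30% have prior injury. Injury risk is 40% with it and 20% without, whatever the score. A low score occurs in 70% with prior injury and 40% without.
- Share with a low score: 0.3 × 0.7 + 0.7 × 0.4 = 0.49
- Prior injury among low scorers: 0.21 / 0.49 = 0.429; among high scorers: 0.09 / 0.51 = 0.176
- Injury risk, low: 0.429 × 0.4 + 0.571 × 0.2 = 0.286; high: 0.176 × 0.4 + 0.824 × 0.2 = 0.235
- HR = ln(1 − 0.286) / ln(1 − 0.235) = 1.25, with 1200 × (0.49 × 0.286 + 0.51 × 0.235) = 312 events
- z = √(312 × 0.49 × 0.51) × ln 1.25 ≈ 2.0, so an unadjusted log-rank test is significant about 52% of the time although the score does nothing within either stratum

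Over prior injury in 20-40%, risk 30-40% with prior injury and a low score in 60-70% with against 40-45% without, the HR runs from 1.05 to 1.28 and the chance of significance from 6% to 61%.

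**4. Split, continuous and adjusted compared.** Simulation with 1200 cadets, 30% prior injury, 20% injured and no effect of the score itself. Percentage of runs significant:

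| Assumed prior-injury HR; fall in score | Median split, unadjusted | Continuous, unadjusted | Continuous, adjusted for prior injury |
|---|---|---|---|
| 1.5; 0.25 SD | 5-6% | 7% | 4-6% |
| 2; 0.5 SD | 13-16% | 23% | 4-6% |
| 2.5; 0.75 SD | 40-47% | 66% | 4-6% |

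With 10-30% injured, the split column becomes 5-6%, 9-20% and 26-57%.

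The last column assumes a single confounder, perfectly measured. Adding to the middle row an unmeasured fitness trait (assumed HR 0.8 or 0.7 per SD, raising the score by 0.25 to 0.5 SD) made the adjusted model significant in 14% to 68% of runs.

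**The case against.** The strongest reply is that items 1 and 2 ask only whether self-efficacy is a predictor. They do not say independent predictor, and an unadjusted association answers that question validly. The combined purpose stands in section 9.6, and the hypotheses promise only exploration. This is right, and it sets the limit of the point: the curve does not contradict Objectives 1 and 2. But the sentence in 9.6 is worded as the purpose of the study, and no analysis serves it.

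Three further replies also stand. A continuous score without adjustment is no protection; in the table it misleads at least as often as the split. Adjustment does not establish independence either, because smoking and aerobic endurance are named in 9.2 but not listed among the baseline data in 10.2. And the power loss assumes a median split, which the plan does not specify.

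A reader might infer that the plan will wrongly declare self-efficacy an independent risk factor. The documents do not support that. They claim no independence and give no data on whether prior injury lowers confidence; under mild confounding the error rate is close to nominal. Differences between the injury source lists in 9.3 and 11.6, and surveillance that runs past CBT, are matters of detail and carry no weight here.

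**Conclusion.** The point holds in a limited form. For injury the plan has one method, it requires an unstated grouping of the score, and it leaves the combined-risk-factor purpose without an analysis although several of the factors are collected. That conclusion rests on the text and needs no simulation.

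The size of the harm is not known. The 36% loss holds for a median split of a normal score. The false-signal rates rest on assumed prevalence, injury risk and confounding, and range from negligible to large. The change is one the sponsor should make. The randomized deadlift comparison is not affected.

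**What to change.** In sections 9.3 and 11.6, replace the method in items 1 and 2 along these lines:

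> The main analysis is a Cox regression of time from the baseline self-efficacy form to first new injury during CBT. The score enters as a continuous term, with a check of linearity. The HR and 95% CI are reported (a) unadjusted, as marginal prediction only, and (b) adjusted for gender, BMI (categories or spline) and prior-year injury. The model is stratified by company. Kaplan-Meier curves by score group are descriptive.

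Also state:
- which of the four impact levels in section 10.1, Phase 2, count as an injury event;
- that only injuries after the form count, and earlier ones are baseline history (the form is completed in week one or two of CBT);
- that follow-up is censored at the end of CBT or on leaving it;
- for Objective 2, that the adjusted model is fitted only for tasks with enough attributed injuries, against a stated minimum, and that these models are exploratory or adjusted for multiplicity;
- that the adjusted result is reported as association beyond the measured factors, not as proof of an independent risk factor.

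Stratification by company is proposed because the education message is allocated by company (section 10.1, Phase 3). Self-reported injuries without an onset date cannot enter a time-to-event model; if there are any, a logistic regression with the same covariates can include them.

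The cost is SAP wording and a little programming. The adjustment variables are already collected and no extra cadets are needed.
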